5.3 Data Presentation Conventions

- 1 year = 365.25 days. Year is calculated as (days/365.25) and will be rounded to 1 digit after the decimal point (tenths) for presentation purposes.
- 1 month = 30.4375 days. Month is calculated as (days/30.4375) and will be rounded to 1 digit after the decimal point (tenths) for presentation purposes.
- 1 pound = 0.454 kg and 1 kg = 2.2 pounds.
- 1 inch = 2.54 cm and 1 cm = 0.3937 inches.
- Body mass index (BMI) calculated as [weight (kg)/height (m)²]

5.4 Study Day

If the date of assessment occurs on or after the first dose date of double-blind study medication, then study day will be calculated as (date of assessment – date of first double-blind dose) + 1. If the date of assessment occurs prior to the first double-blind dose date, then study day will be calculated as (date of assessment – date of first double-blind dose). There is no study day 0.

5.5 Baseline Definition

Baseline data are defined as data collected which are prior to the administration of the first dose. If there is more than one value on or prior to Study Day -1, the value closest to and prior to the receipt of the first dose, whether scheduled or unscheduled, will be used as the Baseline value.

The baseline of the average of the daily average NRS pain intensity score will be the average of the scores during the baseline pain assessment period which is 7 consecutive days prior to the first dose of study medication.

5.6 Analysis Visit Windows

Assessment nominal visit window will be applied.

5.6.1 Unscheduled Assessments

Both scheduled and unscheduled assessments, including the assessments at early termination visits, will be considered for planned timepoint summaries based on the above analysis visit windowing rules. All assessments will be presented in data listings.

5.6.2 Multiple Measurements within Visit Windows

In the event that more than one assessment falls within a given window, the assessment closest to the target study day will be selected for the by-visit analysis. If two assessments are equidistant from the target study day, then the chronologically last assessment will be used. Exceptions may be made for incomplete assessments, in which case, more complete assessments may be given priority. Details are provided in a separate programming conventions document.

For safety analyses where the most extreme values should be selected, e.g. overall post-baseline minimum, overall post-baseline maximum, and potentially clinically important values for overall post-Baseline summaries, all non-missing post-Baseline values should be considered, regardless of whether the value is selected for the by-visit summaries. All results will be presented in data listings.

5.7 Missing or Incomplete Date for Last Dose of Study Drug

For subjects with completely missing last dose date, the last dose date will be imputed by the last expected dosing date, defined as the earliest of the following dates: last dose administer date + scheduled dosing interval per protocol, EOT/ET date.

For subjects with partial missing last dose date, the imputation will be compared against the last expected dosing date as defined above. Detailed algorithms will be documented in a separate programming specifications document. The missing or incomplete dates will be displayed in the data listings as reported on the eCRF rather than the imputed dates.

5.8 Missing or Incomplete Dates for Concomitant or Post-Treatment Medications

Missing or incomplete medication start or end dates will be imputed for the purpose of determining whether the medications are taken concomitantly (see [Section 11](#) for definition). When the chronological order of medication use relative to the study drug treatment period is unclear due to missing or incomplete date(s), the medication will be considered as concomitant. The imputation algorithms will be detailed in the analysis dataset specification document. The missing or incomplete dates will be displayed in the data listings as reported on the eCRF rather than the imputed dates.

5.9 Missing or Incomplete Dates for Adverse Events

Missing or incomplete adverse event (AE) start dates will be imputed for the purpose of determining whether the AEs are treatment-emergent (see [Section 14.1](#) for definition). When the chronological order of an AE onset relative to the study drug treatment period is unclear due to missing or incomplete date(s), the AE will be considered as treatment-emergent. The imputation algorithms will be detailed in the analysis dataset specification document. The missing or incomplete dates will be displayed in the data listings as reported on the eCRF rather than the imputed dates.

5.10 Missing Severity Assessment for Adverse Events

If the severity is missing for a treatment-emergent AE, a severity of “Severe” will be assigned. The imputed values for severity assessment will be used for incidence summaries, and the actual values will be presented in data listings.

5.11 Missing Relationship to Study Drug for Adverse Events

If the relationship to study drug is missing for a treatment-emergent AE, a causality of “Related” will be assigned. The imputed values for relationship to study drug will be used for incidence summaries, and the actual values will be presented in data listings.

5.12 Character Values of Clinical Laboratory Variables

If the reported value of a clinical laboratory variable cannot be used in a summary due to, for example, a character string reported for a numeric variable, an appropriately determined coded value will be used in the summary. The coding algorithms will be detailed in the analysis dataset specification document. The actual values as reported in the database will be presented in data listings.

6 SUBJECT DISPOSITION

For subjects who participate in the screening phase but are not randomized (screen failures), their demographics information (including age, sex, and primary race), screen failure reasons

(the specific inclusion/exclusion criterion (or criteria) not met or other reasons including the reason due to the COVID-19 public health emergency (PHE) and protocol version will be listed. If a subject is re-screened, then the re-screening subject ID and the final enrollment status (whether eventually enrolled) will also be displayed in this listing. In addition, the frequency that the screen failure reasons are reported will be summarized. Note that one subject may be deemed ineligible for multiple inclusion/exclusion criteria and may be allowed to rescreen with the permission of the Medical Monitor, provided the screen failure was due to a temporary condition that subsequently resolved.

The number of sites that screened at least 1 subject, number of sites that randomized at least 1 subject, number of subjects screened, and number of unique subjects screened will be tabulated. In addition, the number of subjects enrolled at each site will also be tabulated by Analysis Set and by treatment group and overall.

The number and percentage of subjects who completed the study, discontinued early (all discontinued and by discontinuation reasons including reason due to the COVID-19 PHE), and the reason for discontinuation will be summarized by treatment group using the Randomized and Full Analysis Sets. All subjects excluded from the Safety, Full Analysis Sets, and the reason(s) for exclusion will be listed.

7 PROTOCOL DEVIATIONS

Protocol deviations will be reviewed periodically over the course of the study. The review process, definition of the deviation categories, and the classification of a deviation as major or minor are detailed in the Protocol Deviation Management Plan. Protocol deviations will also be assessed with respect to relationship to the COVID-19 PHE. A summary of the number and percentage of subjects with major protocol deviations for each deviation category will be presented by treatment group for the Randomized Analysis Set in three ways: all protocol deviations, COVID-19-PHE related protocol deviations, and non-COVID 19-PHE related protocol deviations. Three data listings of all protocol deviations, COVID-19-PHE related protocol deviations, and non-COVID-19-PHE related protocol deviations will be provided.

8 DEMOGRAPHICS AND OTHER BASELINE CHARACTERISTICS

Demographics and Baseline characteristics will be summarized for the Safety Analysis Set using descriptive statistics. Variables include age, age group (18-40 years and >40 years), sex, primary race, ethnicity, height, weight, and body mass index (BMI).

Race will also be categorized by White vs. Non-White. The eCRF reported age reflects a subject's age at the Baseline visit date.

9 MEDICAL HISTORY

Medical history data will be coded using Medical Dictionary for Regulatory activities (MedDRA) version 23.0. The subject incidence will be summarized for each system organ class (SOC) and preferred term for the Safety Analysis Set. A subject will be counted only once per SOC or per preferred term for the summary.

A listing of the SOC, preferred term, body system, verbatim term for the medical history condition/event, start and stop dates (when available), and an indicator for whether or not the condition is ongoing will be provided.

10 EXTENT OF EXPOSURE AND TREATMENT COMPLIANCE

Summaries of exposure and compliance to study drug will be provided for the Safety Analysis Set.

10.1 Exposure to Study Drug

The number of doses dosed, the number of morning doses dosed, the number of missed doses, the number of missed morning doses, and the number of total tablets dosed will be summarized.

10.2 Treatment Compliance

Study drug compliance will be calculated as the number of tablets taken, divided by the expected number of tablets taken*100.

Treatment compliance will be summarized as a categorical variable. The number and percentage of subjects within each of the following compliance levels will be tabulated: <80%, 80 to 120% and >120%.

The number of missed doses and the number of missed morning doses will be summarized as a categorical variable.

11 CONCOMITANT AND POST-TREATMENT MEDICATION

Prior medication is defined as any medication with stop dates prior to the date of the first dose of study drug. Concomitant medication is defined as any medications that are ongoing at the first dose of study drug or with a start date between the dates of the first and last doses of study drug, inclusive. Post-treatment medication is defined as any medication with a start date after the date of the last dose of study drug. Medications will be coded using WHO Drug Global Dictionary March 2020 or newer version.

The number and percentage of subjects taking prior, concomitant and post-treatment medications will be tabulated separately by each drug class (ATC Level 3) and medication preferred term, treatment group and overall for Safety Analysis Set. Multiple medication

usage by a subject in the same category will be counted only once. Listings of the prior, concomitant and post-treatment medications will also be provided.

COVID-19 Public Health Emergency (PHE) Related Medications

Concomitant medication analyses described above will also be tabulated and listed by relationship to the COVID-19 PHE (Not related to the COVID-19-PHE vs. Related to the COVID-19-PHE).

12 EFFICACY ANALYSES

Unless otherwise specified, all efficacy analyses will be performed using the planned treatment assignments based on the randomization schedule for the Full Analysis Set.

12.1 Efficacy Variables

Primary Efficacy Endpoint

- Change from Baseline to Week 4 in the average of the daily average Numeric Rating Scale (NRS) pain intensity scores

Key Secondary Efficacy Endpoints

- Patient Global Impression of Change (PGIC) at Week 4 with reference to baseline status
- Change from Baseline to Week 4 in Western Ontario and McMaster Universities Osteoarthritis Index (WOMAC) total score and individual subscale scores for pain, stiffness, and physical function
- Proportion of subjects who are responders as defined by 30% and 50% reduction from Baseline to Week 4 in the average of the daily average NRS pain intensity scores

Additional Secondary Efficacy Endpoints

Change from Baseline to every study visit in:

- Weekly average of the daily worst NRS pain intensity scores
- Brief Pain Inventory–Short Form (BPI-sf)
- 12-item Short Form Survey (SF-12)

Exploratory Endpoints

- Comparison of average daily rescue medication use
- Hospital Anxiety and Depression Scale (HADS)

12.2 Adjustment for Covariates

The baseline average of daily average pain score as a covariate in the model.

12.3 Handling of Missing Data

Weekly Mean Pain Intensity Scores

If a subject reports at least 3 days with non-missing pain intensity scores within a particular week, the weekly mean pain intensity score will be derived using the non-missing scores only. This is identical to imputing the missing scores as the mean of the non-missing scores. If the subject reports less than 3 days with non-missing pain intensity scores within a particular week, the weekly mean pain intensity score will be treated as missing data.

Missing weekly mean pain intensity scores will be imputed using multiple missing data and pattern mixture methodology as detailed in Section 13. Sensitivity analyses will be conducted exploring different patterns for missing data.

WOMAC Index Total Score

If at least 50% of items within a subscale are non-missing, the missing items of the WOMAC score at a weekly visit will be imputed using the mean of non-missing items within the same subscale. Otherwise, the item, the subscale score and the total score will all remain missing. The total and subscale scores will be derived as the sum of all respective observed and imputed scores. If all values of a particular subscale are missing at a particular week then the total and corresponding subscale score will be treated as missing.

12.4 Multiple Comparisons / Multiplicity

The primary efficacy endpoint is change from baseline to week 4 in the average of the daily average Numeric Rating Scale (NRS) pain intensity scores. For the primary efficacy analysis, the null hypothesis is that there is no treatment effect between 400 mg QID and placebo during the study versus the alternative hypothesis that there is a treatment effect. Similar hypothesis applies to the comparison of 800 mg BID to placebo.

The overall Type I error is controlled by a hierarchical testing procedure. The procedure is to test the difference of the treatment effect between 400 mg QID versus placebo first, at significant level $\alpha=0.05$. If this test is significant, then comparison for 800 mg BID versus placebo will be performed at $\alpha=0.05$ level.

12.5 Examination of Subgroups

No subgroup analyses for primary endpoint are planned.

13 METHODS OF EFFICACY ANALYSES

13.1 Primary Efficacy Endpoints

13.1.1 Primary Efficacy Endpoints

Estimand

The primary estimand has the following attributes:

- Population: all randomized subjects who received at least one dose of study drug and with baseline pain assessments and at least one post-baseline pain assessment.
- Endpoint: change from baseline to week 4 in the average of the daily average Numeric Rating Scale (NRS) pain intensity scores
- Intercurrent events: premature discontinuation from the study, the hypothetical estimand is to evaluate the pharmacological effect as if no withdrawals had occurred.
- Treatment condition: one of the randomized treatment groups of the following per protocol: 1600 mg total dose (provided as 2×800 mg tablets), 1600 mg total dose (provided as 4×400 mg tablets), or placebo.
- Population-level summary: difference in mean of endpoint between treatment conditions.

Statistical Hypotheses

The primary endpoint is the change from baseline to week 4 in the average of the daily average Numeric Rating Scale (NRS) pain intensity scores.

The mean change from baseline to week 4 daily average NRS score will be compared between each of the ACP-044 dose groups (400 mg QID, 800 mg BID) to the placebo group.

The null hypothesis is the mean change from baseline to week 4 in the average of the daily average Numeric Rating Scale (NRS) pain intensity scores using ACP-044 is equal to that of placebo in subjects with pain associated with osteoarthritis of the knee.

The alternative hypothesis is the mean change from baseline to week 4 in the average of the daily average Numeric Rating Scale (NRS) pain intensity scores using ACP-044 is not equal to that of placebo in subjects with pain associated with osteoarthritis of the knee.

Primary Estimator

The primary efficacy variable will be analyzed using an analysis of covariance model (ANCOVA) based on the FAS with treatment, sex, and baseline K-L score (randomization strata) as factors and baseline weekly average of daily average pain score as a covariate in the model. The primary comparison will be between each ACP-044 dose group versus the

placebo group. The comparison between the average of the means of the two ACP-044 dose groups versus the mean of placebo group will also be conducted. Missing data will be imputed using multiple imputation based on missing at random assumption (MAR) with an exception of missing data from subjects who are treated with ACP-044 and discontinue the study due to lack of efficacy or adverse events. Their missing data will be imputed using the data from placebo group.

13.1.2 Sensitivity Analyses

No sensitivity analyses are planned for primary efficacy endpoint.

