9.5.2 Primary Analyses

The primary efficacy variable will be analyzed using an analysis of covariance model (ANCOVA) based on the FAS with treatment, sex, and baseline K-L score (randomization strata) as factors and baseline weekly average of daily average pain score as a covariate in the model. The primary comparison will be between each ACP-044 dose group versus the placebo group. The comparison between the average of the means of the two ACP-044 dose groups versus the mean of placebo group will also be conducted. Missing data will be imputed using multiple imputation based on missing at random assumption (MAR) with an exception of missing data from subjects who are treated with ACP-044 and discontinue the study due to lack of efficacy or adverse events. Their missing data will be imputed using the data from placebo group. The details of missing data imputation and multiplicity adjustment will be described in the SAP.

Sensitivity analysis using pattern mixture model and tipping point approach with multiple imputation to impute missing data will be performed to assess the robustness of the results due to treatment discontinuation and other intercurrent events.

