5 DATA HANDLING CONVENTIONS

All data collected in the study will be listed.

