19 CHANGES TO ANALYSES SPECIFIED IN PROTOCOL

Due to early termination of the ACP-044 program, the changes to the planned analyses are:

- Primary efficacy endpoint will be analyzed using an analysis of covariance model (ANCOVA) based on the FAS with treatment, sex, and baseline K-L score (randomization strata) as main factors and baseline weekly average of daily average pain score as a covariate in the model. The missing data will be imputed using baseline observed data carried forward (BOCF).
- Key secondary efficacy endpoints, the observed data will be provided in descriptive statistics including point estimates and listings.
- Secondary efficacy endpoints, the observed data will be provided in descriptive statistics and listings, no statistical inferences will be applied.
- Exploratory efficacy endpoints, the observed data will be provided in descriptive statistics and listings, no statistical inferences will be applied.

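### The SAP drops the Protocol's sensitivity analyses of the primary result without listing the change, contradicts itself on the missing-data rule, and leaves rescue out of the estimand

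*SAP*

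**What the plan says.** **Sensitivity analyses.** Protocol 9.5.2, repeated in the synopsis, commits to a pattern mixture model and a tipping point approach, both with multiple imputation, "to assess the robustness of the results due to treatment discontinuation and other intercurrent events". SAP 13.1.2 states "No sensitivity analyses are planned for primary efficacy endpoint", and 13.1.3 adds no supportive analysis. SAP 12.3 nevertheless states "Sensitivity analyses will be conducted exploring different patterns for missing data". Section 19 opens with "Due to early termination of the ACP-044 program, the changes to the planned analyses are" and then gives four bullets, on the primary, key secondary, secondary and exploratory endpoints. None mentions sensitivity analyses.

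**Missing-data rule.** SAP 13.1.1 specifies multiple imputation under MAR, with placebo-based imputation for ACP-044 subjects who stop for inefficacy or an adverse event. SAP 12.3 also refers to multiple imputation and pattern mixture methods, to be detailed in section 13. Section 19 replaces this with BOCF.

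**Estimand and rescue.** The estimand in 13.1.1 has one entry of this kind: "Intercurrent events: premature discontinuation from the study, the hypothetical estimand is to evaluate the pharmacological effect as if no withdrawals had occurred". Acetaminophen is allowed through Week 4 (Protocol 3.1.3, SAP 3.1), and Protocol 6.4.1 and SAP 5.2.1 both describe it as confounding for efficacy. SAP 12.3 says that, with at least 3 diary days in the week, "the weekly mean pain intensity score will be derived using the non-missing scores only"; it makes no exception for days with rescue. The only rescue analysis is a study-wide mean daily tablet count (13.4), and section 19 makes it descriptive: "Exploratory efficacy endpoints, the observed data will be provided in descriptive statistics and listings, no statistical inferences will be applied".

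**The concern.** Sections 12.3 and 13.1.2 cannot both be followed, and neither can 13.1.1 and 19. A reader who uses section 19 to learn what changed would find the move to BOCF but not the loss of the robustness checks, and would find the opposite in 12.3.

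The two conflicts compound each other. The imputation rule for the primary endpoint was changed in the same document that removed every check on it. BOCF gives each subject without a Week 4 mean a change of zero, which is not the effect had nobody withdrawn. The estimate reported and the estimand written down are therefore different quantities, and nothing planned shows how far apart they are.

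Rescue is a smaller, separate gap. The estimand refers to a pharmacological effect but is silent on an analgesic that subjects may take in the endpoint week. If use differs by arm, the Week 4 difference mixes drug and acetaminophen. That is an acceptable target if it is declared, and here it is not.

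**Working it through.** **1. The plan's own figure.** Inputs (Protocol 9.3, SAP 3.5): difference 0.85, SD 1.7, two-sample t-test, two-sided 0.05, 20% discontinuation. Exact t-test power is 0.795 at 63 per arm and 0.801 at 64. 64 / (1 − 0.20) = 80 per arm, and 3 × 80 = 240. The stated sample size reproduces, so 0.85 and 20% are used below.

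**2. The passages side by side.**

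| Place | Sensitivity analyses | Primary missing-data rule |
|---|---|---|
| Protocol 9.5.2 | Pattern mixture and tipping point | MI, placebo-based for some drug-arm dropouts |
| SAP 12.3 | To be conducted | MI and pattern mixture |
| SAP 13.1.1 | – | MI, as in the Protocol |
| SAP 13.1.2 | None | – |
| SAP 19 | Not mentioned | BOCF |

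**3. What BOCF can do to the estimate.** Let p be the mean placebo improvement, p + 0.85 the mean drug improvement, and mD and mP the shares missing at Week 4. Assume that those missing would have improved as much as those observed. BOCF sets their change to zero, so the expected difference is

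(1 − mD)(p + 0.85) − (1 − mP)p.

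- 20% missing in both arms: 0.80 × 0.85 = 0.68, whatever p is.
- 30% on drug, 10% on placebo: p = 1 gives 0.70 × 1.85 − 0.90 × 1 = 0.395; p = 2 gives 0.70 × 2.85 − 0.90 × 2 = 0.195.
- 10% on drug, 30% on placebo: p = 1 gives 0.90 × 1.85 − 0.70 × 1 = 0.965; p = 2 gives 0.90 × 2.85 − 0.70 × 2 = 1.165.

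The 20% is the documents' discontinuation rate. The unequal rates and p are assumptions. The bias can go either way.

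**4. Precision at the actual size.** SAP section 1 gives 61 randomized, about 20 per arm. SE = 1.7 × √(2/20) = 0.54; the 95% CI half-width is about 1.1 points; power for 0.85 is about 34%. The shift of 0.85 − 0.68 = 0.17 is about 0.3 of an SE. The largest shift shown, 0.85 − 0.195 = 0.655, is about 1.2 SE.

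**5. Rescue.** The documents give no rescue rates. Approximately, shift = (excess of rescue on placebo) × (effect of rescue on the score), and it is zero if the arms use rescue equally. An excess of 0 to 13 percentage points of Week 4 days, with an effect of 0.5 to 1.0, gives 0 to 0.13 points. An excess of 10 to 30 points of subjects, with an effect of 0.5 to 1.5, gives 0.05 to 0.45. The spread shows that the size depends on the assumptions.

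**The case against.** The best defence is that the trial stopped on 8 August 2022 and the SAP is dated 21 September 2022. A tipping point analysis of 61 subjects has little to tip, and cutting the analysis back was reasonable. Nor was the removal concealed: 13.1.2 states it outright. Both points stand against any suggestion of concealment. Neither removes the conflict with 12.3, and neither explains why section 19, which gives termination as the reason for its changes, leaves this one out.

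On rescue, three stronger readings are tempting and the documents do not support them.

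- A reader might infer that the Protocol's sensitivity analyses would have dealt with rescue, since they cover other intercurrent events. They impute missing data and do not name rescue, so they would have reached it only if a rescue pattern had been defined.
- A reader might infer that an imbalance in rescue would stay hidden. It would not: use is summarized by arm, and "All data collected in the study will be listed". What is missing is a link between Week 4 rescue and the primary estimate.
- A reader might infer that rescue materially biases the result. Without rates in the documents, that cannot be claimed.

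It could also be said that the primary ANCOVA is the only efficacy inference left. Section 19 rules out inference for the secondary and exploratory endpoints. For the key secondaries it only prescribes descriptive statistics with point estimates, so this is a fair reading but not a stated rule.

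**Conclusion.** The point holds on the text alone: a Protocol commitment is dropped, one SAP section denies it, another still promises it, and the change list omits it. The same change list contradicts 13.1.1 on the primary missing-data rule. The discontinuation side is the more important one. BOCF alone moves 0.85 to 0.68 at the planned dropout rate in both arms, and to between 0.20 and 1.17 under the unequal dropout assumed above. These figures assume that those missing would have improved as much as those observed; step 4 also keeps the planning SD of 1.7, which BOCF would alter.

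The rescue side is an undeclared strategy of unknown size, possibly zero. Its wording also needs work. Rescue is barred in the baseline week (Protocol 3.1.2) yet supplied for it (Protocol 5.1.3). Stopping before visits is mandatory in Protocol 3.1.3 and SAP 3.1 but only encouraged in SAP 5.2.1.

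It would go too far to infer that a significance verdict or a confirmatory claim is at risk. At about 34% power the trial cannot carry one. What is affected is how an imprecise estimate is read. The SAP should be corrected, but the retained primary analysis need not change.

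**What to change.** 1. **Restore a discontinuation check.** In 13.1.2, plan the Protocol's imputation rule (MAR, with placebo-based imputation for ACP-044 subjects who stop for inefficacy or an adverse event) as a sensitivity analysis beside the BOCF ANCOVA, with estimate and CI for the same contrasts. Say how each rule relates to the estimand; the placebo-based part does not match the no-withdrawal target exactly either.
2. **Make 12.3, 13.1.1, 13.1.2 and 19 agree** on the primary missing-data rule and on which sensitivity analyses are run. List in section 19, with the reason, each Protocol sensitivity analysis that is dropped.
3. **Declare rescue.** State in 13.1.1 that it is handled by treatment policy, and report Week 4 rescue days by arm beside the primary estimate. An analysis adding a fixed amount to scores on rescue days is optional. If run, keep it to one or two amounts and treat baseline-week rescue in the same way.
4. **Reconcile the rescue passages** named in the verdict. Which rule should apply is for the sponsor; none is proposed here.

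The cost is SAP wording, one table and a few model fits on eDiary data already recorded daily (Protocol 6.6). No new data are needed and the primary result does not change. The limit is size: at 20% missing, about 20 × 0.20 = 4 subjects per arm would be imputed, so the imputation model must be simple and the result read as descriptive. If the SAP can no longer be amended, Protocol 9.1 already provides for describing and justifying deviations in the clinical study report.
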